## 1.7. Potential Risks of CC-90001 and the Study Population

Based on the Phase 1 studies in healthy subjects and the Phase 1b study in pulmonary fibrosis subjects, the TEAEs associated with administration of CC-90001 are mostly gastrointestinal in nature. Gastrointestinal TEAEs reported in these studies included nausea, diarrhea, indigestion, abdominal discomfort/cramping, emesis, and constipation. Headache, rash, dermatitis, fatigue and musculoskeletal pain TEAEs were also reported. The majority of the reported TEAEs were mild or moderate in severity. Some subjects who experienced nausea in the Phase 1 studies have reported less nausea when the IP was taken with food. There were no SAEs reported in the Phase 1 studies.

The Sponsor has instituted extensive safety monitoring into this protocol based upon potential risks associated with CC-90001 and the disease under study.

- Frequent study visits to assess safety laboratory results, including, but not limited to, liver function, white blood cell (WBC) count, hemoglobin, total cholesterol, high density lipoprotein (HDL), low density lipoprotein (LDL), triglycerides, pulmonary function and arterial oxygen saturation (SpO2).
- Individual subject dose stopping rules and study stopping rules to ensure subjects are discontinued from CC-90001 in the event of severe liver toxicity. In a study conducted with the structurally unrelated pan-JNK inhibitor, CC-930, IPF subjects treated with high doses of CC-930 demonstrated abnormal liver function tests after approximately 8-12 weeks of daily dosing. In order to support this Phase 2 study with chronic dosing, the CC-90001-CP-003 study in pulmonary fibrosis subjects was conducted to understand the safety profile after a 12-week treatment duration.
- CC-90001 may be an inhibitor of liver transporters (eg, OATP1B1 and OATP1B3) and breast cancer resistance protein (BCRP). Therefore, subjects taking statins

concomitantly with CC-90001 may experience increased plasma concentrations of statins with prescribed doses. To ensure the safety of the subjects, concomitant statins will be dose adjusted to a therapeutic level (see Section 8.2.1).

- Urine cytology to examine for abnormal cellular findings.
- Electrocardiograms (ECGs) with centralized over-read and blood pressure measurements will be performed to monitor for potential cardiovascular effects.

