**Table 5: Table of Events (Continued)**

Visit(s) k	Screening Phase	24-Week Double-Blind Placebo-Controlled Treatment Phase			80-Week Active Treatment Extension Phase				Early Termination Visit	Post-Treatment Observational Follow-up
	1 Screening	2 Baseline a	3	4-9 Every 4 Weeks	10E	11E-17E Every 4 Weeks	18E-25E Every 6 Weeks	26E End of Treatment		27E
Week(s)	-8 to -1	0	1 ± 3 days	4, 8, 12, 16, 20, 24 ± 3 days	25 ± 3 days	28, 32, 36, 40, 44, 48, 52 ± 3 days	58, 64, 70, 76, 82, 88, 94, 100 ± 3 days	104 ± 3 days		108 4-weeks post-treatment ± 3 days
Complete Physical Examination	X	-	-	-	X	-	-	X	X	X
Targeted Physical Examination	-	X	X	X	-	X	X	-	-	-
Vital Signs	X	X	-	Week 24	-	Week 52	Week 76	X	X	X
Weight	X	-	-	Week 24	-	-	-	X	X	X
Height	X	-	-	-	-	-	-	-	-	-
12-Lead ECG	X	-	-	Weeks 4, 12, 24	-	Week 52	-	X	X	X
Hematology Laboratory	X	X	X	X	X	X	X	X	X	X
Chemistry Laboratory	X	X	X	X	X	X	X	X	X	X

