## 6.2. Treatment Phase

The subject will begin treatment upon confirmation of eligibility at the Baseline (Visit 2). For all subsequent visits, an administrative window of  $\pm 3$  days is permitted. Scheduling of Visits 3 to 9 is based on Visit 2 (randomization date) and scheduling of Visits 10E to 26E is based on Visit 9 (re-randomization date).

The following evaluations will be performed at the frequency specified in the Table of Events, [Table 5](#) and in the order described below. The evaluations should be performed prior to dosing on the visit day, unless otherwise specified.

- Adverse event evaluation
- Concomitant medications reviewed with the subject
- Concomitant procedures reviewed with the subject
- Patient-reported outcome questionnaires will be completed as described in [Section 6.7](#)
- Assessment for new or worsening shortness of breath

As part of the routine assessments during the study visit, subjects will be assessed for new or worsening of shortness of breath (SOB). The Investigator should use his/her clinical judgement to decide how to further assess and treat such subjects.

Subjects who experience and receive adequate treatment for SOB with permitted drugs (see [Section 8.1.2](#)) but demonstrate further clinical decline and/or decrease of  $\geq 10\%$  from baseline in % predicted FVC at two consecutive evaluations at a minimum of 4 weeks between evaluations should discontinue IP and enter the 4-week Post-treatment Observational Follow-up Phase (Table of Events, [Table 5](#)). Whether to discontinue a subject from study treatment who experiences unexplained worsening in hypoxemia (an absolute decrease from baseline of 4% or more in SpO2) will be left up to the Investigator's discretion. Treatment of subjects during the Post-treatment Observational Follow-up Phase is at the discretion of the Investigator.

All relevant clinical data (summary on clinical course, signs and symptoms; laboratory, lung function and imaging results; and treatment provided) relating to new or worsening shortness of breath must be collected by the Investigator. Changes in respiratory status that are considered by the Investigator as possibly or likely due to [REDACTED] disease progression will be reviewed further by the independent Adjudication Committee. Details regarding the adjudication process will be described in a separate charter.

- Efficacy assessments as described in [Section 6.4](#)

- 

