- 12-lead ECG will be performed as described in Section 6.1
  - Complete/targeted physical examination (source documented only): Complete physical examinations will include evaluation of the skin, nasal cavities, eyes and ears, respiratory, cardiovascular, abdominal, neurological, lymphatic, and musculoskeletal systems. Gynecological, urogenital and rectal examinations will not be performed unless for cause.

A targeted physical examination includes evaluation of the respiratory, cardiovascular, abdominal systems. Clinically significant abnormal findings identified during the physical examinations will be recorded on the CRF as adverse events. Gynecological, urogenital and rectal examinations will not be done unless for cause.

- Vital signs: Vital sign measurements (body temperature, pulse rate, respiration rate, and seated blood pressure) will be taken. If an abnormal (out of range) value constitutes an adverse finding, it should be reported as an AE if appropriate.
- Weight (to be done in street clothes, no shoes) will be measured and recorded.
- Clinical laboratory safety tests will be performed as described in Section 6.1, with the exception of those labs performed only at Screening (eg, QuantiFERON-TB Gold®, hepatitis test, and postmenopausal testing).

- 
- Counseling about pregnancy precautions and the potential risks of fetal exposure must be conducted.
  - Study IP dispensation (refer to Section 7.2 and the Table of Events, Table 5), returns (all used and unused blister cards) and IP compliance will be assessed.

A more detailed description of the order of the procedures for each visit will be provided in the operations manual.

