**Subjects are instructed to take 2 tablets once daily, approximately the same time of day, with or without food.**

The IPF study subjects are provided with the following IP treatments:

- **24-week Double-blind, Placebo-controlled Treatment Phase: Baseline (Visit 2) to Week 24 (Visit 9)**

Subjects will receive 2 tablets once daily as follows:

- CC-90001 400 mg PO QD (two 200 mg tablets)
- CC-90001 200 mg PO QD (one 200 mg tablet and one placebo tablet)
- Placebo PO QD (two placebo tablets)

*Note: The first dose of IP is taken on the day of Visit 2 and the last dose of IP is taken on the day of Visit 9.*

- **80-week Active Treatment Extension Phase: Week 24 + 1 Day (Day After Visit 9) to Week 104 (Visit 26E)**

Subjects will receive 2 tablets once daily as follows:

- CC-90001 400 mg PO QD (two 200 mg tablets)
- CC-90001 200 mg PO QD (one 200 mg tablet and one placebo tablet)

*Note: The first dose of IP is taken on the day after Visit 9 and the last dose is taken at Visit 26E.*

At Visit 9/Week 24, all IPF subjects originally randomized to placebo at baseline during the 24-week Double-blind Placebo-controlled Treatment Phase will be re-randomized 1:1 to receive blinded CC-90001 (200 mg or 400 mg PO QD) via IWRS during the 80-week Active Treatment Extension Phase. All subjects originally randomized to CC-90001 (200 mg or 400 mg PO QD) will remain on that same blinded treatment assignment. Subjects begin the blinded-dose active treatment the day after Visit 9 (ie, Week 24 + 1 day). During the 80-week Active Treatment Extension Phase, all subjects not on concurrent protocol-allowable

SOC therapy will have the opportunity, if deemed appropriate by the Investigator, to receive allowed SOC [REDACTED].

The PPF substudy subjects are provided with the following IP treatments:

- **24-week Double-blind, Placebo-controlled Treatment Phase: Baseline (Visit 2) to Week 24 (Visit 9)**

Subjects will receive 2 tablets once daily as follows:

- CC-90001 PO QD (400 mg PO QD [two 200 mg tablets], unless review of benefit-risk favors 200 mg PO QD)
- Placebo PO QD (two placebo tablets)

*Note: The first dose of IP is taken on the day of Visit 2 and the last dose of IP is taken on the day of Visit 9.*

- **80-week Active Treatment Extension Phase: Week 24 + 1 Day (Day After Visit 9) to Week 104 (Visit 26E)**

Subjects will receive 2 tablets once daily as follows:

- CC-90001 PO QD (400 mg PO QD [two 200 mg tablets], unless review of benefit-risk favors 200 mg PO QD)

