### 8.2.1. Statins

Due to the potential for DDIs, the following must be done to ensure the safety of subjects taking statins while on the study:

- During the Screening phase of the study, all subjects receiving statins should be prescribed the lowest approved statin dose for adults approximately 1 week before Visit 2 (Baseline). For example, a subject receiving atorvastatin 20 mg during the Screening Period should be instructed to begin taking atorvastatin 10 mg, instead, approximately 1 week prior to randomization.

*Note: Subjects who are already receiving the lowest approved statin dose for adults should remain on that dose.*

- At Visit 2 (Baseline), eligible subjects will begin treatment with CC-90001. Following multiple oral doses of CC-90001, the steady state should be achieved on approximately Day 5.
- At Visit 3, the lipid profile will be assessed. Based on results of the subjects' lipid profile at Visit 3, the statin dose may be increased to the next highest approved dose, if indicated.

*Note: If the lipid profile at Visit 3 is comparable to the lipid profile from Visit 1 (Screening), the statin dose should not be increased.*

- At Visit 4, the lipid profile will be assessed. Based on the subjects' lipid profile at Visit 4, the statin dose may be increased to the next approved dose, if indicated.

*Note: If the lipid profile at Visit 4 is comparable to the lipid profile from Visit 1 (Screening), the statin dose should not be increased.*

The Investigator should use his/her clinical judgement to decide when/if the further increase in the statin dose is warranted and how to assess these subjects. **In particular, Investigators should monitor closely for AEs associated with increased statin exposures (eg, myalgia, liver function test abnormalities).** If needed, the Investigator should refer the subject to his/her general practitioner or other appropriate healthcare provider for further follow-up.

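### Table 5 schedules no on-drug blood pressure before Week 24, and neither blood pressure nor ECG for about 28 weeks after placebo subjects start CC-90001

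*Combined protocol and SAP*

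**What the plan says.** Section 1.7 lists the safety monitoring built into the protocol. On the cardiovascular side it says: "Electrocardiograms (ECGs) with centralized over-read and blood pressure measurements will be performed to monitor for potential cardiovascular effects". It gives no interval for either measure.

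Section 6.2 places blood pressure inside vital signs: "Vital sign measurements (body temperature, pulse rate, respiration rate, and seated blood pressure) will be taken". The two rows of Table 5 that matter are "Vital Signs X X - Week 24 - Week 52 Week 76 X X X" and "12-Lead ECG X - - Weeks 4, 12, 24 - Week 52 - X X X". Read against the column heads, they give:

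- Vital signs at Screening, Baseline, Weeks 24, 52, 76 and 104, early termination and follow-up.
- ECG at Screening, Weeks 4, 12, 24, 52 and 104, early termination and follow-up.

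Section 6.2 also sets the order on visit days: "The evaluations should be performed prior to dosing on the visit day, unless otherwise specified". For subjects moving from placebo to active drug, Section 7.2 says: "Subjects begin the blinded-dose active treatment the day after Visit 9 (ie, Week 24 + 1 day".

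Appendix E requires a blood pressure before each six-minute walk test (6MWT). Its procedure puts the walk at randomization and then at 24-week intervals. Table 5 instead puts the walk at Weeks 24, 52, 76 and 104, as do the 6MWT timeframes in Table 2.

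**The concern.** Of the two measures named for the same purpose, the ECG is repeated early (Weeks 4 and 12) and blood pressure is not. Section 8.2.1 says of repeated dosing that "the steady state should be achieved on approximately Day 5", so subjects are at full exposure for most of 24 weeks before a scheduled reading. The early ECG times are also not repeated when placebo subjects first receive the drug.

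Three things are at stake.

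- **The placebo-controlled comparison.** Vital signs belong to the secondary safety endpoint (Table 2), and Section 9.7 summarizes them by visit. In the first 24 weeks that summary has one scheduled on-treatment time point, which only subjects still attending can supply. Early termination readings come at scattered times.
- **The exposure-period summary.** Section 9.7 combines subjects treated from Day 1 with subjects who switched. Scheduled ECGs at 4 and 12 weeks of exposure exist only for the first group.
- **Permitted co-medication.** Section 8.1.1 allows hypertension drugs. Section 8.2 asks for close monitoring of substrates of the transporters that CC-90001 may inhibit, and Appendix H lists valsartan, olmesartan, telmisartan and aliskiren among such substrates. No scheduled blood pressure before Week 24 supports that monitoring.

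**Working it through.** The plan states no figure to reproduce here. The check is arithmetic on the visit schedule.

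**Inputs**
- Post-baseline visits (Table 5): Weeks 1, 4, 8, 12, 16, 20, 24; then 25, 28, 32, 36, 40, 44, 48, 52; then every six weeks to 100; then 104.
- Vital signs and ECG weeks as listed above.
- First active dose: day of Visit 2 in the original active arms, Week 24 + 1 day after a switch (Section 7.2).
- Anchors (Section 6.2): "Scheduling of Visits 3 to 9 is based on Visit 2 (randomization date) and scheduling of Visits 10E to 26E is based on Visit 9". The window is ±3 days. The window on Visit 9 therefore does not carry into the post-switch interval.

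**Original active arms.** Baseline assessments precede the first dose, so the Baseline blood pressure is off drug. The next scheduled one is at Week 24. Visits in between: Weeks 1, 4, 8, 12, 16, 20 = 6. The first on-drug ECG is at Week 4.

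**Switched placebo subjects.** First active dose = 24 × 7 + 1 = day 169, counted from Visit 2 with Visit 9 on its nominal date. The Week 24 vital signs and ECG precede that dose. The next of each is at Week 52 = 52 × 7 = day 364.
- Interval = 364 − 169 = 195 days; 195 / 7 = 27.9 weeks.
- With the ±3-day window: 192 / 7 = 27.4 to 198 / 7 = 28.3 weeks.
- Visits in between: Weeks 25, 28, 32, 36, 40, 44, 48 = 7.

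**Pre-walk blood pressure.** Under Table 5 the walk falls at the same weeks as vital signs and adds no new time point. Under Appendix E it would fall at Week 48 = day 336, and (336 − 169) / 7 = 167 / 7 = 23.9 weeks after first active dose. In the first 24 weeks Appendix E adds nothing before Week 24. It has no bearing on the ECG.

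**Effect of adding vital signs at Weeks 4, 12, 28 and 36**

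| First scheduled on-drug blood pressure | Now | With the change |
|---|---|---|
| Original active arms | Week 24 | Week 4 |
| Switched subjects | 195 days after first active dose | 28 × 7 − 169 = 27 days |

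Week 36 is 36 × 7 − 169 = 83 days after the switched subject's first active dose. Weeks 28 and 36 thus match, to within a day, the 4 and 12 weeks of exposure at which the original arms have ECGs.

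**Subjects affected by the post-switch gap.** Up to 55 in the IPF study, and about 15 more if the PPF substudy opens.

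**The case against.** Section 1.7 says only that the measurements will be made, and Table 5 makes them. The reference to frequency in that list concerns visits for laboratory results, lung function and oxygen saturation. A reader might infer that the protocol contradicts itself, but the text does not support that. What remains is a choice of timing.

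A reader might also infer that switched subjects go unobserved for cardiovascular effects. They do not. A physical examination that includes the cardiovascular system is scheduled at every visit from Week 25 to Week 52. Clinically significant findings become adverse events, and adverse events are collected continuously. Early termination includes vital signs and ECG, and Section 9.7 brings unscheduled readings into the summaries. This narrows the point without closing it. The targeted examination does not list blood pressure and is kept in source documents only, while early termination and unscheduled readings depend on withdrawal or clinical suspicion.

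The visible text reports no blood pressure signal. The early events in Section 1.7 are mostly gastrointestinal, the compound background is redacted, and the results of the 12-week study in pulmonary fibrosis are not given in detail. The sponsor may hold data that justify sparse readings. The Day 5 statement comes from the statin section and does not say when a blood pressure effect would appear.

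Finally, the placebo-controlled phase already gives ECGs at Weeks 4, 12 and 24 on about 110 active and 55 placebo subjects. Switched subjects add uncontrolled, descriptive data at the same doses. That limits what extra post-switch ECGs would contribute, and is why they are left optional below.

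**Conclusion.** The point stands as a schedule gap that is cheap to close. Table 5 has no scheduled on-drug blood pressure before Week 24, across six attended visits. Subjects switched from placebo have no scheduled vital signs or ECG until Week 52, 27.9 weeks after first active dose (27.4 to 28.3 with the visit window).

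This rests on three assumptions: Table 5 governs the walk test, the subject stays on treatment, and only scheduled assessments are counted. If Appendix E governs the walk, the first post-switch blood pressure moves to Week 48 (23.9 weeks) and the ECG stays at Week 52. Appendix E does not say that the pre-walk reading is entered in the case report form.

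The documents do not support reading this as an absence of cardiovascular data, as a breach of Section 1.7, or as evidence of a missed safety signal. The PPF count applies only if enrollment into the substudy begins after the first interim analysis.

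**What to change.** In Table 5, add vital signs for all subjects at Visits 4 and 6 (Weeks 4 and 12, alongside the ECGs already taken) and at Visits 11E and 13E (Weeks 28 and 36). Applying this to every subject keeps the schedule identical across arms, so it reveals nothing about who switched. Reconcile the 6MWT timing in Appendix E with Table 5. ECGs at Visits 11E and 13E are optional: they would close the post-switch ECG gap at the price of two more centrally read recordings per subject, which the sponsor can weigh separately.

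The cost of the main change is four cuff readings per subject at visits already attended, plus a protocol amendment. Unless it is classed as administrative, the amendment needs ethics approval (Section 13.5), and subjects must be re-consented if the consent form changes (Section 13.3). The change concerns assessment timing only and sets no dose or treatment rule.

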## 2. STUDY OBJECTIVES AND ENDPOINTS

**Table 1: Study Objectives**

Primary Objective
To evaluate the effect of CC-90001, 200 mg and 400 mg, when orally administered (PO) once daily (QD), compared with placebo, on percent of predicted forced vital capacity (FVC) after 24 weeks of treatment in subjects with idiopathic pulmonary fibrosis (IPF).
Secondary Objectives
To evaluate the effects of CC-90001, 200 mg and 400 mg PO QD, compared to placebo, after 24 weeks of treatment in subjects with IPF, on: 

• FVC (milliliters [mL])

• Six-minute Walk Test (6MWT)

• Disease progression

• Health-related quality of life: St. George's Respiratory Questionnaire (SGRQ) and University of California San Diego-Shortness of Breath Questionnaire (UCSD-SOBQ)

• Dose response

• Safety and tolerability

To examine the effect of CC-90001 PO QD, compared to placebo, in subjects with progressive pulmonary fibrosis (PPF), on: 

• Safety and tolerability

**Table 1: Study Objectives (Continued)**

**Table 1: Study Objectives (Continued)**

**Table 2: Idiopathic Pulmonary Fibrosis Study Endpoints**

Endpoint	Name	Description	Timeframe
Primary	Forced vital capacity (FVC)	Percentage point difference in % predicted FVC	Baseline to Week 24
Secondary	FVC	Absolute change and rate of decline in FVC (expressed in mL)	Baseline through Week 24
Secondary	6-minute Walk Test (6MWT) with Borg Scale	Change in the distance walked during the 6MWT as measured in meters (m) Change in dyspnea rating on Borg Scale	Baseline to Week 24; Baseline to Week 52; Baseline to Week 76; Baseline to Week 104; Week 24 to Week 52; Week 24 to Week 104
Secondary	Disease progression	Disease progression is defined as one or more of the following: 
 
• Death from respiratory failure, or
 
• Absolute decrease of <math>\geq 10\%</math> from baseline in % predicted FVC at two consecutive evaluations at a minimum of 4 weeks between evaluations, or
 
• Decrease from baseline of <math>\geq 50</math> meters in 6MWT distance (in the absence of a readily explainable cause, such as injury or trauma), or
 
• Unexplained worsening hypoxemia (an absolute decrease from baseline of 4% or more in arterial oxygen saturation by pulse oximetry [SpO2]).
 
	Baseline through Week 24
Secondary	Quality of life	Change from Baseline in total score and domains on the Saint George's Respiratory Questionnaire (SGRQ)	Baseline through Week 24
		Change from Baseline in the University of California San Diego Shortness of Breath Questionnaire (UCSD- SOBQ)	Baseline through Week 24

**Table 2: Idiopathic Pulmonary Fibrosis Study Endpoints (Continued)**

Endpoint	Name	Description	Timeframe
Secondary	Safety and tolerability	Type, frequency, severity, and relationship of adverse events (AEs), clinical laboratory tests including urine cytology, 12-lead electrocardiogram (ECG), vital signs, and physical examination	Signing of the informed consent form through Week 108 (4-week post-treatment observational follow-up)

[figure not shown]

**Table 3: Progressive Pulmonary Fibrosis Substudy Endpoints**

Endpoint	Name	Description	Timeframe
Secondary	Safety and tolerability	Type, frequency, severity, and relationship of adverse events (AEs), clinical laboratory tests including urine cytology, 12-lead electrocardiogram (ECG), vital signs, and physical examination	Signing of the informed consent form through Week 108 (4-week post-treatment observational follow-up)

